4.5. Pharmacokinetic and Pharmacokinetic/Pharmacodynamic Methods

Pharmacokinetic (PK), pharmacodynamic (PD), and PK/PD analysis are the responsibility of Lilly's PK/PD group.

A population PK approach using nonlinear mixed-effects modeling will be used to analyze LY3819469 concentration data.

Exposure-response analysis between LY3819469 concentration and Lp(a) levels may be performed using population PK/PD nonlinear mixed-effects modeling techniques implemented on Nonlinear Mixed Effects Modeling (NONMEM) software.

Additionally, the impact of intrinsic and extrinsic factors, such as age, weight, gender, and renal function, on PK and PD parameters, may be examined as needed.

If antidrug antibody (ADA) titers are detected from immunogenicity testing, then the impact of immunogenicity titers on LY3819469 PK or any relevant efficacy parameters may also be examined. Additional analyses may be conducted if they are deemed appropriate.

4.6. Immunogenicity

At the visits and times specified in the protocol schedule of activities (Section 1.3), venous blood samples will be collected (if local regulations and ethical review boards allow) and stored for potential future analysis to determine antibody production against LY3819469. If the data is available at the time of final database lock, the following analysis will be conducted.

Treatment-emergent antidrug antibodies (TE ADAs) are defined as those with a titer 2-fold (1 dilution) greater than the minimum required dilution if no ADAs were detected at baseline (treatment-induced ADA) or those with a 4-fold (2 dilutions) increase in titer compared to baseline if ADAs were detected at baseline (treatment-boosted ADA). A patient is evaluable for TE ADA if the patient has a nonmissing baseline ADA result, and at least 1 nonmissing postbaseline ADA result.

A listing of ADA results and TE ADA status at each visit will be provided, including ADA screening test result (detected/not detected) and the titer for detected samples.

The frequency and percentage of patients with preexisting ADA and with TE ADA will be tabulated by dose (if data warrant), where proportions are relative to the number of patients who are TE ADA evaluable. The frequency and percentage of patients with hypersensitivity and injection site reaction treatment-emergent adverse events (TEAEs) by TE ADA status will be tabulated if data warrant.

4.7. Tertiary/Exploratory Endpoints Analysis

4.7.1. Bayesian Analyses for Dose-Response

The longitudinal Nonmonotone Exponential Time (NEXT) model will be applied to model the longitudinal dose-response following a single dose of LY3819469. The model is appropriate for a situation when the response reaches the maximum effect and starts to deteriorate. It can be used to evaluate the durability of the treatment after a single dose of a potent and durable treatment such as LY3819469. The 2-component prediction (ITP) model proposed in Fu et al. (2010) and Qu et al. (2019) can be considered a special case of the NEXT model. The model is as follows:

$$Y_{dit} = \beta_0 Baseline + f(t; \beta_1, \beta_2)(\lambda(d) + \delta_{di}) + \epsilon_{dit},$$

where Y_{dit} represents the observation for subject *i* at time *t* when taking dose *d*, $\lambda(d)$ is the mean dose response function for dose *d*, δ_{di} is the between-subject random error term, ϵ_{dit} is the within-subject random error term. The mean response function $f(t; \beta_1, \beta_2)$ is modeled as

$$f(t;\beta_1,\beta_2) = \frac{1-e^{-\beta_1 t}}{1+\beta_2 t},$$

where β_1 controls the rate of change of the response curve and β_2 controls the time to maximum treatment effect.

A 3-parameter logistic regression model may be assumed for the dose response function, $\lambda(d)$. Let α_0 , α_1 , and α_2 represent the basal effect when the dose level is 0 (placebo), the maximum effect that can be achieved by any dose level on top of placebo, and the dose level that produces half of the maximum improvement, respectively. Then, the mean function of the parameter of interest is modeled by

$$\lambda(d) = \alpha_0 + \frac{\alpha_1 d}{\alpha_2 + d}.$$

The estimation of the parameters will be carried out in a Bayesian framework assuming noninformative priors for the hyperparameters in the model as follows:

$$\begin{cases} \alpha_0, \alpha_1 \sim N(0, 100^2), \\ \alpha_2 \sim U(0, 400), \\ \frac{1}{\sigma^2} \sim Gamma(0.01, 0.01), \\ \beta_0, \beta_1, \beta_2 \sim N(0, 100^2). \end{cases}$$

Posterior inference will be drawn for the dose-response of clinical interest and the 95% credible intervals will also be plotted.

Other dose-response models for f(d) may be explored if the aforementioned dose-response models do not fit the data well, for example, Simple Normal Dynamic Linear Modeling (NDLM) described below

$$\begin{cases} f(d_1) \sim N(0, \tau) \\ f(d_{i+1}) \sim N(f(d_1), \tau), i = 1, 2 \dots \end{cases}$$

where 1,2,... are the indexes of each *i*th dose level. The first dose level prior takes on a normal distribution with a mean of 0 and a precision of τ . τ is drawn from either a normal or gamma distribution. Subsequent dose levels take on a normal distribution with the mean of the previous dose level and precision τ .

Variations of the NEXT model may be explored to model the longitudinal dose-response following a second dose of LY3819469.

4.8. Safety Analyses

Unless specified otherwise, safety assessments will be guided by an estimand comparing safety of LY3819469 doses with placebo irrespective of adherence to intervention. Thus, safety analyses will be conducted using the FAS. Safety assessments may also pool the 2 LY3819469 400-mg treatment groups, where appropriate.

4.8.1. Extent of Exposure

Duration of exposure will be calculated as number of days subject was "on-treatment" as defined in Section 4.1. Summary of duration of exposure (defined as time in days from date of randomization to the date of the last study visit) will be provided by treatment group using data from FAS. The following descriptive statistics will be provided: n, mean, SD, median, minimum, maximum, and sum (that is, total participant-years of follow-up). In addition, the number of subjects who received 1 or 2 doses will be summarized by counts and percentages.

4.8.2. Adverse Events

A TEAE is defined as an event that first occurred or worsened in severity after first dose. The Medical Dictionary for Regulatory Activities (MedDRA) low level term (LLT) will be used in the treatment-emergent derivation. The maximum severity for each LLT during the baseline period including ongoing medical history will be used as baseline severity. Events with a missing baseline severity will be treated as "mild" in severity for determining treatment-emergence. Events with a missing severity during the postbaseline period will be treated as "severe" and treatment-emergence will be determined by comparing to baseline severity.

For events occurring on the day of first taking study medication, the case report form collected information (for example, treatment emergent flag, start time of study treatment and event) will be used to determine whether the event was pre- versus post-treatment if available. If the relevant information is not available, then the events will be counted as posttreatment.

The counts and percentages of participants with TEAEs will be summarized by treatment using MedDRA preferred terms (PTs) nested within system organ class (SOC). Statistical comparisons will be applied at both the SOC and PT levels. Events will be ordered by decreasing frequency within SOC. The SOC will be in alphabetical order. For events that are sex-specific, the denominator and computation of the percentage will include only participants from the given sex.

An overview of the number and percentage of participants who experienced a TEAE, a serious adverse event (SAE), or death, participants who discontinued from study treatment or study due to an AE, and relationship to study drug will be summarized by treatment.

The counts and percentages of patients with TEAEs by maximum severity will be summarized by treatment using MedDRA PT. For each participant and TEAE, the maximum severity for the MedDRA PT is the maximum postbaseline severity observed from all associated LLTs mapping to the MedDRA PT. The maximum severity will be determined based on the nonmissing severities. If all severities are missing for the defined postbaseline period of interest, it will show as missing in the table.

4.8.3. Patient Narratives

Patient narratives will be provided for all participants who experience any of the following "notable" events:

- death
- serious AE, or
- permanent discontinuation of study treatment due to AEs.

Patient narratives (patient level data and summary paragraph) will be provided for participants in the randomized population with at least 1 notable event.

4.8.4. Vital Signs

If multiple records of an individual's vital signs are collected at the same visit, they will be averaged prior to being used for data summaries and analyses.

Descriptive summaries by treatment and by nominal visit will be provided for baseline and postbaseline values as well as change from baseline values.

Treatment differences in mean change will be analyzed using the MMRM model as described in Section 4.4.2 for the FAS.

Counts and percentages of participants with treatment-emergent abnormal sitting systolic blood pressure (BP), sitting diastolic BP, and pulse rate will be presented by treatment group. Both planned and unplanned measurements will be included in the analysis. The criteria for identifying patients with treatment-emergent vital sign abnormalities are stated in Table EZEB.4.6.

Table EZEB.4.6.Categorical Criteria for Abnormal Treatment-Emergent Blood
Pressure and Pulse Measurements

Parameter	Low	High
Systolic BP (mm Hg)	≤90 and decrease from	≥129 and increase from
(sitting)	baseline ≥20	baseline ≥20
Diastolic BP (mm Hg)	≤50 and decrease from	≥90 and increase from
(sitting)	baseline ≥10	baseline ≥10
Pulse (bpm)	<50 and decrease from	>100 and increase from
(sitting)	baseline ≥15	baseline ≥15

Abbreviation: BP = blood pressure.

Counts and percentages of participants with maximum systolic BP and diastolic BP will be summarized by treatment groups for the following categories using safety participants.

Systolic BP (mm Hg)	Diastolic BP (mm Hg)
<90	<60
≥90	>60
≥120	>90
≥140	>110
≥160	≥120
≥180	

Abbreviation: BP = blood pressure.

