4.11. Changes to Protocol-Planned Analyses

Extend the time periods of interest for first secondary objective regarding time-averaged Lp(a) lowering.

5. Sample Size Determination

The sample size calculation is based on the primary estimand and its endpoint, and the percent change from baseline in time-averaged Lp(a) over Days 60 to 180.

Approximately 254 participants will be randomly assigned in a 1:2:2:2:2 ratio to LY3819469 16 mg 2 doses, 96 mg 2 doses, 400 mg 2 doses, 400 mg 1 dose plus placebo 1 dose, and placebo 2 doses. Assuming a 15% dropout rate, this results in approximately 24 completers for the 16-mg group and 48 completers per arm for the rest of the groups.

Assuming a SD of 20%, and a 2-sided alpha level of 0.05, the completers for each treatment arm will provide >99% power to detect a treatment difference of 70% reduction for the primary endpoint of LY3819469 versus placebo. The sample size was determined appropriate to provide a sufficient amount of safety data.

6. Supporting Documentation

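### The diastolic rows of the maximum blood-pressure table mix > and ≥, so a maximum of exactly 60 mm Hg has no row and exactly 90 or 110 is left out of the row that starts there

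*SAP*

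**What the plan says.** SAP Section 4.8.4 (Vital Signs) contains two categorical blood-pressure displays.

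The first, Table EZEB.4.6, defines treatment-emergent abnormal values by a threshold and a change together:

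- High diastolic pressure is "≥90 and increase from" baseline of at least 10 mm Hg.
- Low systolic pressure is "≤90 and decrease from" baseline of at least 20.
- Low diastolic pressure is "≤50 and decrease from" baseline of at least 10.

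For this analysis, "Both planned and unplanned measurements will be included in the analysis".

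The second display has no table number and follows directly: "Counts and percentages of participants with maximum systolic BP and diastolic BP will be summarized by treatment groups for the following categories". Its rows, in mm Hg, are:

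- systolic: <90, ≥90, ≥120, ≥140, ≥160, ≥180
- diastolic: <60, >60, >90, >110, ≥120

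The text does not label any row of the second display as low pressure or hypotension, and it does not mention a minimum.

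**The concern.** The systolic column uses one convention throughout: a < row at the bottom, then ≥ rows. The diastolic column opens with <60, moves to three strict > rows and ends with an inclusive ≥120. A programmer who follows the printed signs will leave a maximum of exactly 60 unclassified and will not count 90 or 110 in the rows named after those values. Blood pressure is usually recorded in whole numbers, so exact values at a cut-off are to be expected.

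A second question is what the <90 and <60 rows are for. They are filled from each participant's maximum, so a participant enters them only if no reading reached the cut-off. Someone scanning a safety table could take them for counts of low pressure, which they are not.

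At stake are the counts in a descriptive safety table and its agreement with the other display in the same section. No hypothesis test on efficacy, error rate or sample size depends on it.

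**Working it through.** The documents state no count or percentage for this table, so there is no plan figure to reproduce. The check is to classify each possible value by the printed rows, and then to gauge how many participants could be affected.

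**Step 1: classify every whole number.** I took diastolic values from 30 to 150 and systolic values from 60 to 240, and read the rows as cumulative because none has an upper limit.

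| Maximum diastolic | Rows entered as printed | Rows entered if written <60, ≥60, ≥90, ≥110, ≥120 |
|---|---|---|
| 59 | <60 | <60 |
| 60 | none | ≥60 |
| 61 | >60 | ≥60 |
| 90 | >60 | ≥60, ≥90 |
| 91 | >60, >90 | ≥60, ≥90 |
| 110 | >60, >90 | ≥60, ≥90, ≥110 |
| 111 | >60, >90, >110 | ≥60, ≥90, ≥110 |
| 120 | all four upper rows | all four upper rows |

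The only diastolic value with no row is 60. No systolic value lacks a row, and systolic <90 is the exact complement of ≥90.

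**Step 2: compare with Table EZEB.4.6.** Take a participant with a normal baseline whose highest diastolic reading is exactly 90, at least 10 above baseline. Table EZEB.4.6 counts this participant as high; the >90 row does not. With ≥90, and the same readings in both displays, everyone who is high in Table EZEB.4.6 is also in the row.

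**Step 3: size at the cut-offs.** The documents give no blood-pressure means or SDs, so these are assumptions. For participant i at visit j, the reading is round(μ + b_i + e_ij), with between-participant SD 8 and within-participant SD 6 for diastolic, and 13 and 9 for systolic. There are 10 postbaseline visits (Visits 3 to 12 in the protocol's Schedule of Activities) and 254 participants (SAP Section 5). The table shows average counts of participants over 400 simulated trials.

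| | μ = 72 diastolic, 120 systolic | μ = 77, 128 | μ = 82, 135 |
|---|---|---|---|
| Maximum diastolic = 60 | 0.64 | 0.14 | 0.02 |
| Maximum diastolic = 90 | 6.92 | 10.54 | 11.58 |
| Maximum diastolic = 110 | 0.06 | 0.30 | 1.18 |
| Maximum diastolic > 90 | 37.13 | 79.78 | 134.64 |
| Maximum diastolic < 60 | 1.60 | 0.33 | 0.02 |
| Minimum diastolic < 60 | 88.74 | 42.94 | 16.51 |
| Maximum systolic < 90 | 0.16 | 0.02 | 0.00 |
| Minimum systolic < 90 | 29.68 | 10.41 | 3.22 |

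Participants at exactly 90 are 6.92/254 = 2.7%, 10.54/254 = 4.1% and 11.58/254 = 4.6% of the trial. As a share of a ≥90 row they are 6.92/(37.13 + 6.92) = 16%, 10.54/(79.78 + 10.54) = 12% and 11.58/(134.64 + 11.58) = 8%.

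**Step 4: what the < rows can show.** The last four lines of the table compare a maximum with a minimum. The gap is what the definitions imply and does not measure an error. It does show that the maximum-based rows will be nearly empty even when many participants have a low reading at some visit.

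**The case against.** The strongest reply is that little is miscounted. A strict cut-off is still a definition: a participant at 90 remains in >60, and one at 110 remains in >60 and >90. Only exactly 60 is lost, and that is expected to affect fewer than one participant. This stands, and it limits the point to an inconsistency of cut-offs. A reader might go further and infer that the whole table's counts are wrong. The documents do not support that, because every systolic row is well defined and one diastolic value alone is unassigned.

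A reader might also infer that the table would report almost no low blood pressure whatever the truth. That is not supported either. The table is announced as a distribution of the maximum, and its bottom rows are correct complements for that statistic. Low pressure has its own criteria in Table EZEB.4.6, and Section 4.8.4 also plans by-visit summaries and a repeated-measures analysis of mean change. One gap remains: Table EZEB.4.6 needs a diastolic value of 50 or less and a fall from baseline. A participant whose lowest diastolic lies between 50 and 60, but who reached 60 at another visit, is therefore shown as low in neither display.

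It is also fair to say that the two displays need not agree. Table EZEB.4.6 requires a rise from baseline, Table EZEB.4.3 restricts it to participants with a normal baseline, and its systolic cut-off of 129 does not appear in the category table. Their counts would differ even with matching signs. The comparison therefore supports consistent handling of the value 90, but it does not imply equal counts.

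Finally, the text was extracted from a PDF, and three ≥ signs could have been read as >. Neighbouring ≥ signs survived, so the printed reading is plausible, but only the source file can settle it.

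**Conclusion.** The point holds as a minor cut-off error in a descriptive safety table. As printed, a maximum diastolic pressure of exactly 60 has no category, and exactly 90 or 110 is excluded from the row that starts there. This is inconsistent with the systolic column, with ≥120 in the same column and with Table EZEB.4.6.

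Under the assumed distributions, about 7 to 12 of 254 participants would move into the 90 row, about 0.1 to 1.2 into the 110 row, and fewer than one would gain a row at 60. These counts assume whole-number readings, 10 postbaseline visits with no missing data, and a maximum taken over those visits. The SAP also says: "If multiple records of an individual's vital signs are collected at the same visit, they will be averaged prior to being used". Such averaging would reduce exact ties where repeats are taken, while rounding of readings to even or zero end digits would increase ties at these cut-offs.

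The <90 and <60 rows are not wrong. They need a label, because they cannot show participants who were low at only some visits. The primary result is unaffected.

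**What to change.** Check the three diastolic > signs against the source PDF. If they are as printed, write the diastolic rows as <60, ≥60, ≥90, ≥110, ≥120. Every value then has a row, and <60 and ≥60 become exact complements. The systolic rows need no change.

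State in the table title or a footnote that the <90 and <60 rows count participants whose maximum stayed below the cut-off. If the table is also meant to show low pressure, add separate, labelled rows based on the postbaseline minimum. Do not refill the existing < rows from the minimum: that would mix two statistics in one column, and a participant could then appear on both sides of a cut-off.

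The cost is a wording change in SAP Section 4.8.4 and the matching change in the table program. No additional data are needed.

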4.8.5. Electrocardiograms

Treatment-emergent qualitative electrocardiogram (ECG) abnormalities are defined as qualitative abnormalities that first occurred after baseline. Qualitative abnormal ECGs will be recorded as an AE. A listing of abnormal qualitative ECGs will be created.

4.8.6. Clinical Laboratory Evaluation

For Lp(a), only nmol/L will be reported. All other laboratory data will be reported in both CN and SI units. Limits from the performing lab will be used to define low and high. Descriptive summaries by treatment and by nominal visit will be provided for the baseline and postbaseline values as well as the change from baseline values.

Observed and change from baseline values for each visit may be displayed in plots for participants who have both a baseline and at least 1 postbaseline planned measurement. Baseline will be the last nonmissing observation prior to taking first study drug. Unplanned measurements will be excluded from plots.

A shift table will be provided including unplanned measurements. The shift table will include the number and percentage of participants within each baseline category (low, normal, high, or missing) versus each postbaseline category (low, normal, high, or missing) by treatment. The proportion of participants shifted will be compared between treatments using Fisher's exact test.

For qualitative laboratory analytes, the counts and percentages of participants with normal and abnormal values will be summarized by treatment.

A listing of abnormal findings will be created for laboratory analyte measurements, including qualitative measures. The listing will include participant identification, treatment group, laboratory collection date, study day, analyte name, and analyte finding.

The MMRM model as described in Section 4.4.2 or ANCOVA (if MMRM model is not applicable due to single postbaseline measurement) will be used for the analysis during the treatment period for the continuous measurements for selected lab tests.

4.8.7. Additional Safety Assessments

4.8.7.1. Hepatobiliary Disorders

The counts and percentages of participants with treatment-emergent potentially drug-related hepatobiliary disorders will be summarized by treatment using the PTs nested within Standardized MedDRA Queries (SMQs). Detailed search criteria can be found in Appendix 6 (Section 6.6).

4.8.7.1.1. Liver Enzymes

Analyses for laboratory analyte measurements are described in Section 4.8.6. This section describes additional analyses of liver enzymes.

Hepatic labs include alanine aminotransferase (ALT), aspartate aminotransferase (AST), total bilirubin (TBL), direct bilirubin (DBL), serum alkaline phosphatase (ALP), international normalized ratio (INR), and gamma-glutamyl transferase (GGT). When criteria are met for hepatic evaluations, investigators will conduct close monitoring of hepatic symptoms and liver tests, perform a comprehensive evaluation for alternative causes of abnormal liver tests, and complete follow-up hepatic safety electronic case report form (eCRFs).

The following will be analyzed for hepatic safety (Table EZEB.4.7):

Table EZEB.4.7. Summary Tables and Figures Related to Hepatic Safety

Analysis	Population or Analysis Set
 Abnormal Postbaseline Categories – Hepatic Safety Parameters ALT The number and percentage of participants with a measurement greater than or equal to 1×, 3×, 5×, 10×, and 20× the performing lab ULN during the treatment period for all participants with a postbaseline value. AST The number and percentage of participants with a measurement greater than or equal to 1×, 3×, 5×, 10×, and 20× the performing lab ULN during the treatment period for all participants with a postbaseline value. AST The number and percentage of participants with a measurement greater than or equal to 1×, 3×, 5×, 10×, and 20× the performing lab ULN during the treatment period for all participants with a postbaseline value. ALP The number and percentage of participants with a measurement greater than or equal to 2× and 3× the performing lab ULN during the treatment period will be summarized for all participants with a postbaseline. TBL The number and percentage of participants with a measurement greater than or equal to 2×, 5×, and 8× the performing lab ULN during the treatment period will be summarized for all participants with a postbaseline value. DBL The number and percentage of participants with a measurement greater than or equal to 2× and 5× the performing lab ULN during the treatment period will be summarized for all participants with a postbaseline value. DBL The number and percentage of participants with a measurement greater than or equal to 2× and 5× the performing lab ULN during the treatment period will be summarized for all participants with a postbaseline value. 	FAS
Hepatocellular Drug-Induced Liver Injury Screening Plot (TBL vs. ALT or AST)	FAS
Hepatocellular Drug-Induced Liver Injury Screening Table	FAS
Cholestatic Drug-Induced Liver Injury Screening Plot (TBL vs. ALP)	FAS
Cholestatic Drug-Induced Liver Injury Screening Table	FAS
Participant profiles will be created for participants meeting criteria for a comprehensive hepatic evaluation (as defined in the protocol). Participant profiles will include demographics, disposition, information collected on the hepatic safety CRFs (where applicable) and a display of study drug exposure, adverse events, medications, blood pressure, heart rate, and the liver-related measurements over time.	

Abbreviations: ALP = alkaline phosphatase; ALT = alanine aminotransferase; AST = aspartate aminotransferase; CRF = case report form; DBL = direct bilirubin; FAS = full analysis set; GGT = gamma-glutamyl transferase; TBL = total bilirubin; ULN = upper limit of normal.

Planned and unplanned measurements will be included. The measurements do not need to be taken at the same blood draw. Maximum baseline will be the maximum nonmissing observation in the baseline period. The maximum value will be the maximum nonmissing value from the postbaseline period. Planned and unplanned measurements will be included.

The primary purpose of the screening plots is to identify participants whose data warrant further review. For these plots, symbols will be used to indicate the randomized treatment.

For individual participants of interest, participant profiles will be reviewed. The review will include which treatment the participant was taking over time, the changes in hepatic labs over time, and the temporal association with potential causes. The review of participant profiles will also include the identification of any potential Hy's law case or potential cholestatic liver injury case that could have been missed by focusing only on the maximum values when determining 30-day time associations.

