- 21. Lipoprotein apheresis within 3 months of Visit 1, or planned during the study.
- 22. Treatment with another investigational drug, biological agent, or device within 1 month of Visit 1, or 5 half-lives of investigational agent, whichever is longer.
- 23. Treatment with any oligonucleotide or siRNA within 9 months of Visit 1.

Prior/Concurrent Clinical Study Experience

24. Are currently enrolled in any other clinical study involving an investigational product or any other type of medical research judged not to be scientifically or medically compatible with this study.

Diagnostic Assessments

- 25. Clinically significant abnormalities in screening laboratory values that would render a participant unsuitable for inclusion in the opinion of the investigator.
- 26. Any of the following abnormalities:
 - a. estimated glomerular filtration rate (eGFR) <30 mL/min/1.73 m²
 - b. alanine aminotransferase (ALT) or aspartate aminotransferase (AST) >3.0x upper limit of normal (ULN)
 - c. bilirubin > 1.5x ULN, except for participants diagnosed with Gilbert's syndrome

Other Exclusions

- 27. Are Eli Lilly and Company (Lilly) employees, or are employees of any third party involved in a study that requires exclusion of their employees.
- 28. Are investigator site personnel directly affiliated with this study and/or their immediate families. Immediate family is defined as a spouse, parent, child, or sibling, whether biological or legally adopted.
- 29. Are pregnant, or intend to become pregnant or to breastfeed during the study.
- 30. Are, in the judgment of the investigator, actively suicidal and therefore deemed to be at significant risk for suicide.

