# Additional hepatic data collection (hepatic safety CRF) in study participants who have abnormal liver tests during the study

Additional hepatic safety data collection in hepatic safety CRF should be performed in study participants who meet 1 or more of the following 5 conditions:

- 1. Elevation of serum ALT to ≥5x ULN on 2 or more consecutive blood tests (if baseline ALT <1.5x ULN)
  - ➤ In participants with baseline ALT ≥1.5x ULN, the threshold is ALT ≥3x baseline on 2 or more consecutive tests
- 2. Elevated TBL to ≥ 2x ULN (if baseline TBL <1.5x ULN) (except for cases of known Gilbert's syndrome)
  - > In participants with baseline TBL  $\geq 1.5x$  ULN, the threshold should be TBL  $\geq 2x$  baseline
- 3. Elevation of serum ALP to ≥2x ULN on 2 or more consecutive blood tests (if baseline ALP <1.5x ULN)
  - ➤ In participants with baseline ALP ≥1.5x ULN, the threshold is ALP ≥2x baseline on 2 or more consecutive blood tests
- 4. Hepatic event considered to be an SAE
- 5. Discontinuation of study drug due to a hepatic event

Note: the interval between the 2 consecutive blood tests should be at least 2 days.

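### Above the normal limit, the liver-test counts in SAP Table EZEB.4.7 do not separate new from pre-existing elevation; stratify them by the maximum baseline that the SAP already defines

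*SAP*

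**What the plan says.** **The counts.** For ALT and for AST, SAP Table EZEB.4.7 lists "The number and percentage of participants with a measurement greater than or equal to 1×, 3×, 5×, 10×, and 20× the performing lab ULN". The denominator is open to any baseline: "during the treatment period for all participants with a postbaseline value". ALP is counted at >=2x and >=3x ULN. TBL is counted as "a measurement greater than or equal to 2×, 5×, and 8× the performing lab ULN". No row has a baseline condition, a multiple of baseline or a Gilbert's exception.

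**Who can enter.** Protocol section 5.2, criterion 26, excludes "alanine aminotransferase (ALT) or aspartate aminotransferase (AST) >3.0x upper limit of normal", so values up to and including 3.0x ULN are eligible. Bilirubin above 1.5x ULN is excluded "except for participants diagnosed with Gilbert's syndrome". Criterion 26 does not mention ALP. Criterion 25 still lets the investigator exclude a person whose screening laboratory values make them unsuitable.

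**How the protocol treats raised baselines.** Section 8.2.3 splits participants at a baseline of 1.5x ULN and judges those above it against their own baseline. For the hepatic CRF, for example, "the threshold is ALT ≥3x baseline on 2 or more consecutive tests". Its TBL trigger at 2x ULN applies "except for cases of known Gilbert's syndrome".

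**What the SAP has in hand.** Directly below the table the SAP states: "Maximum baseline will be the maximum nonmissing observation in the baseline period". No count listed in the table says that it uses this quantity.

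**The concern.** A count headed as abnormal postbaseline results is normally read as what happened on treatment. Here it mixes two groups: participants whose liver tests rose after dosing, and participants who entered with raised tests and stayed there. If the second group is counted, a real drug effect is diluted. In a small arm, a chance difference in who entered with raised values can imitate or hide a signal.

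The trial is meant to support Phase 3 dose selection, and both documents justify its size by the safety data it will provide. The liver table should therefore show which elevations are new.

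**Working it through.** The documents give no rate, power or sample size for the hepatic counts, so there is no figure of the plan's own to reproduce.

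**Step 1. Which rows can an eligible value reach without changing?** Compare the entry limit with each cut-point.

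| Row in Table EZEB.4.7 | Entry limit (criterion 26) | Reached by an unchanged value? |
|---|---|---|
| ALT/AST >=1x | <=3.0x ULN | Yes, by any value from 1.0x to 3.0x |
| ALT/AST >=3x | <=3.0x ULN | Only at exactly 3.0x; otherwise by fluctuation from just below |
| ALT/AST >=5x, 10x, 20x | <=3.0x ULN | No |
| ALP >=2x, 3x | none stated | Not ruled out |
| TBL >=2x, 5x, 8x, no Gilbert's | <=1.5x ULN | No |
| TBL >=2x, 5x, 8x, Gilbert's | no numeric limit | Not ruled out |

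**Step 2. Do other displays separate new from carried-over elevation?**

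- The treatment-emergent laboratory analysis (SAP section 4.1 and Table EZEB.4.3, row 1.2) requires a normal baseline and takes the most extreme baseline value. It answers the question at the normal limit and omits everyone who entered above it.
- The shift table (SAP section 4.8.6) is by arm but has only low, normal and high. A move from 1.2x to 6x ULN is high to high.
- Participant profiles follow the protocol's baseline-dependent criteria, but they are individual displays.
- The two drug-induced liver injury screening tables are listed without cut-points, a baseline rule or a Gilbert's flag.

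The >=1x rows are therefore largely covered. ALT/AST >=3x, ALP >=2x and TBL >=2x are not covered by any by-arm display with stated cut-points.

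**Step 3. How many participants?** The documents give no liver-test distribution, so these inputs are assumptions: median ALT 0.5 to 0.6x ULN, between-person log SD 0.45 to 0.55, within-person log SD 0.15 to 0.30. The Schedule of Activities gives two predose chemistry panels (Visits 1 and 2) and eight scheduled postbaseline panels (Visits 3, 4, 5, 7, 8, 9, 11 and 12). I simulated 1,000,000 people per combination, kept those with Visit 1 ALT <=3.0x ULN, and drew all later values around the same true level, so there is no drug effect.

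- Counted at >=1x ULN: 15% to 44%. Of these, 45% to 72% were already >=1x before dosing.
- Counted at >=3x ULN: 0.024% to 1.74%. That is 254 x 0.00024 = 0.06 to 254 x 0.0174 = 4.4 participants in the whole trial, and 28 x 0.00024 = 0.01 to 28 x 0.0174 = 0.5 in the 16-mg arm.
- Of those counted at >=3x, 82% to 100% had a maximum baseline >=1.5x ULN.
- Entering at 2 to 3x ULN: 0.17% to 2.25%, or 0.4 to 5.7 of 254. Each has a 12% to 34% chance of being counted at >=3x with no change in true level.
- With maximum baseline 1.5 to 3x ULN, 0% to 2.3% reach twice that baseline.

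The documents give no basis for similar figures for ALP or for Gilbert's participants.

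**Step 4. What does carry-over do to a comparison?** Let q be the share counted because of a pre-existing value and r the rate of new elevation among the rest. The tabulated rate is q + (1 - q)r. Assume r = 5% on placebo (about 56) and 15% on pooled 400 mg (about 113).

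| q (assumed) | Placebo | 400 mg | Apparent risk ratio | Power (normal approx.) |
|---|---|---|---|---|
| 0 | 0.050 | 0.150 | 3.0 | 47% |
| 5% | 0.050 + 0.950 x 0.05 = 0.098 | 0.193 | 1.97 | 34% |
| 10% | 0.145 | 0.235 | 1.62 | 26% |
| 20% | 0.240 | 0.320 | 1.33 | 18% |

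Values of q this large belong to the >=1x rows. At >=3x, q is far smaller under the Step 3 assumptions.

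**Step 5. Small arms.** 254/9 = 28.2 participants at 16 mg, so one carried-over participant is 1/28 = 3.6 percentage points.

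**The case against.** The best defence is that Table EZEB.4.7 is a descriptive screen. It is headed as postbaseline categories, not as treatment-emergent events, and specifies no test. Section 4.8.7.1.1 is stated to be additional to the general laboratory analyses, which do use baseline. Randomization balances pre-existing elevation in expectation. The affected cells above the normal limit are almost empty, and high conditional percentages, such as 82% to 100%, describe a handful of people. The 3.6-point step is true of any count in a 28-person arm. All of this stands, and it limits the point.

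A reader might also infer more than the documents support:

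- *That the SAP as a whole ignores baseline.* It does not. The treatment-emergent analysis, the shift table and the participant profiles all use it.
- *That 15% to 44% measures the problem.* That figure arises at >=1x ULN, where two other displays already answer the question.
- *That these are the only by-arm counts at multiples of ULN.* This cannot be established, because the contents of the screening tables are not specified. Maximum baseline may be meant for those displays.
- *That the SAP contradicts the protocol.* The section 8.2.3 criteria trigger monitoring, evaluation and data collection. They are not analysis definitions, and the two-consecutive-test rule governs CRF completion for ALT and ALP only. Counting a single value is not an error.
- *That Gilbert's participants face no bilirubin limit at all.* They face no numeric limit; criterion 25 still applies.

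The defence does not supply a by-arm display that separates new from old elevation at the higher multiples. The shift table cannot do so, and the treatment-emergent analysis omits the participants in question.

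**Conclusion.** The point holds in a narrow form. Pre-existing elevation can be counted in the ALT/AST >=1x rows, the ALT/AST >=3x rows (at exactly 3.0x, or by ordinary fluctuation from 2 to 3x), the ALP rows, and the TBL rows for Gilbert's participants. Unchanged ALT/AST values cannot reach 5x or above. Since the >=1x rows are largely covered elsewhere, the remaining gap lies at the higher multiples.

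The consequence is dilution and chance imbalance in small arms. A reading of systematic bias between arms is not supported, because the same counting rule applies to every randomized arm. The number affected is probably a handful of participants. That rests on the assumed ALT distribution; Gilbert's prevalence, Gilbert's bilirubin levels and the ALP distribution are unknown. Priority is low: a cheap improvement, between optional and recommended.

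**What to change.** In Table EZEB.4.7, keep the all-participant rows and add:

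1. The ALT/AST, ALP and TBL counts by maximum-baseline category for that test (<1.5x and >=1.5x ULN), using the definition already printed below the table.
2. For the >=1.5x group, multiples of baseline as reporting categories: ALT/AST >=2x and >=3x, ALP >=2x, TBL >=1.5x and >=2x baseline. These match the multiples in protocol section 8.2.3.
3. A separate TBL row for participants with known Gilbert's syndrome, and a flag for them in the drug-induced liver injury screening plots and tables.

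The cost is SAP wording and some extra rows. No new data are needed, because two predose chemistry panels are scheduled and a Gilbert's diagnosis is needed to apply criterion 26 and belongs in the medical history. The drawback is sparse cells in the raised-baseline rows. This changes reporting only; the protocol's monitoring and interruption rules are untouched.
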